5.0 Study Design

The purpose of the following randomized control trial is to determine: 1) the feasibility and usability of the Brain CareNotes mobile application (BCN) intervention to deliver ecological momentary assessment (EMA) surveillance of Behavioral and Psychological Symptoms of Dementia (BPSD) and caregiver distress in amnestic mild cognitive impairment (aMCI) or Alzheimer's Disease (AD) caregivers, 2) the optimal surveillance frequency and 3) whether improved BPSD surveillance can improve opportunities to intervene.

The BCN intervention delivers the Neuropsychiatric Inventory Questionnaire (NPI-Q) to caregivers of patients with either aMCI or AD to monitor BPSD and caregiver distress. During the study caregivers in the intervention group will be asked to answer an EMA version of the NPI-Q on the BCN intervention at differing intervals (weekly or monthly).

We propose to enroll 154 aMCI and AD patient-caregiver dyads from our memory care practice at Eskenazi Health, Sandra Eskenazi Center for Brain Care Innovation (SECBCI), an urban safety net hospital in Indianapolis in a 6-month randomized controlled trial of EMA assessment to monitor BPSD compared to enhanced care. Subject dyads will be randomized to either the intervention or control group in a 1:1 ratio (77 per group). The control group will not receive the BCN intervention. However, the caregivers in the control group will be administered most of the same assessments at the baseline, 3-month and final (6-month) visit as the caregivers in the intervention group, except for the two assessments that ask questions related to the mobile application. Caregivers will also participate in semi-structured interview at the baseline visit, final visit and when triggered by "clinically significant" BPSD.

The study design includes six 1-month periods. Those in the intervention group will be nested in a 2 x 6 cross-over design in which they will be randomly assigned to start with 1 of 2 schedules of EMA surveillance frequency (1) weekly or (2) monthly. The intervention participants will then cross-over at the end of each and every month to the other surveillance frequency condition, over a 6-month time horizon. The crossover design allows efficient sample size reduction for the comparison between two higher frequency arms by allowing persons to serve as their own controls for a within person intervention effect. According to standard analysis of cross-over trials, the comparison

[figure not shown]

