of the two EMA surveillance frequency conditions within the intervention group will be tested with a within-subjects test. Co-variates and biological variation including sex will be incorporated into the analysis.

Table 1. Study Characteristics

Stage of Behavioral Intervention Development:	Stage II
NIH Phase III Clinical Trial?	No
Multiple Site Trial?	No
Brief Description of Study Design	
Study participants, 154 caregiver-patient dyads with amnestic mild cognitive impairment (aMCI) or Alzheimer's Disease (AD) Dementia (308 human subjects) will be randomly assigned to Enhanced Care (EC, 77 dyads) or the BCN Intervention + EC (77 dyads).	
Enhanced Care (EC) x (6-mo)	
 • Dementia collaborative care provided through the Sandra Eskenazi Center for Brain Care Innovation (SECBCI). • Services include care coordination, and evidenced based assessment and treat protocols for behavioral and psychological symptoms of dementia (BPSD).
Brain CareNotes (BCN) App + EC x (6-mo)	
 • The Brain CareNotes (BCN) app was developed with a user centered design for patients with MCI and AD, caregivers and healthcare team members. • The BCN app will deliver the Neuropsychiatric Inventory Questionnaire (NPI-Q) to the caregiver to report on the patient's BPSD severity and associated caregiver distress severity. • The NPI-Q delivery frequency will alternate every 30 days between conditions of weekly or monthly delivery. These set frequencies of weekly and monthly, will be re-evaluated and possibly modified based on feedback from the first 10 participants in the intervention arm. • If BPSD as measured by the NPI-Q rises to a set severity threshold then this data will be shared with the patient's treatment team who will contact the caregiver for further evaluation.

Table 2. Defining Clinically Significant BPSD and Responses to BPSD

Clinically Significant BPSD Severity Threshold	
 Clinically Significant BPSD will be defined as when any NPI-Q severity domain = 3 regardless of caregiver distress, or whenever NPI-Q caregiver distress is marked as “moderate” “severe” or “very severe”.

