6.2 Preliminary Work: Neuropsychiatric Inventory Questionnaire (NPI-Q) –

Ecological Momentary Assessment (EMA) Caregiver Pilot: We successfully pilot tested the NPIQ-EMA app in four AD patient-caregiver dyads without any attrition. The time horizon for the pilot differs from the proposal in that the caregiver was asked to fill out the smartphone survey (NPIQ-EMA) daily for a 2-week time period. Patient ages ranged from 63 to 95, and caregiver ages ranged from 63 – 82. Three of four caregivers identified as African American. All four caregivers found answering the NPIQ-EMA questions to “Not be burdensome.” Several caregivers reported that the NPIQ-EMA improved their awareness of the patient’s BPSD. Three of four answered that they would prefer weekly monitoring rather than daily and the last caregiver expressed a preference for daily monitoring. All caregivers agreed that the system was easy to use.

6.3 Recruitment, Screening, Informed Consent, and Enrollment: The Sandra Eskenazi Center for Brain Care Innovation provides longitudinal care to ~ 600 patients; 38.7% are Black; and 70.4% are female. In addition, each of five clinicians completes an initial assessment on 1-3 new patients per week. We anticipate a recruitment number of 154 dyads over 27 months and believe this to be achievable. Half of the dyads would be randomized to the intervention or treatment as usual group. Our group has a recruitment rate of approximately 50% of eligible subjects in this environment⁴³.

6.4 Randomization Scheme: Participating dyads will be randomized to the two groups (intervention vs control) using a randomization list that contains group assignment in blocks, thus ensuring that the groups have comparable sample sizes throughout the study. We will use a stratified block random assignment following the Kernan strata determination formula (Kernan et al. 1999) listed as, $\# \text{ of strata} < n / B \times 4$, where B is block size and “... n is the sample size at the first planned interim analysis and 4 is a safety factor that accounts for unequal distribution of patients among strata.” Using $n=154$ and $B=4$, then, the $\# \text{ of strata} < 9$. In this study, we will use 8 strata = 2 Diagnosis (aMCI, AD) x 2 Gender (M, F) x Age (< 65, \geq 65). Sealed envelopes with randomization assignments will be prepared by a research team member not involved

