randomization group they are in, the study team member will deliver a plastic bin which contains a binder with paper copies of the assessments and other study related materials. It will be delivered to the patient and caregiver's respective homes without direct contact from team members (left outside home). If the dyad has been randomized to Group 2- The Three Assessments and Mobile Application and request to use a study mobile phone, this will be included in the plastic bin. The purpose of the study binder is to ensure the dyad is able to follow along during the assessment. The study team members will have a mirror binder where they will indicate the caregiver's responses to the assessment questions.

- The study team member will then arrange a time for the caregiver to complete the baseline study visit. The baseline study visit will be completed over the telephone or if the caregiver prefers in-person at the Eskenazi Health, Fifth Third Building located on the Eskenazi Health Hospital Campus (the in-person visit is entirely optional).
- The patient will not be present or participate in the baseline, 3-month or Final / 6-month research visit.
 - During the informed consent visit, patients who have the capacity to consent will consent to the HIPAA authorization form, which grants the study team permission to access their Eskenazi Health medical record and to communicate with their SECBCI clinical team. If they do not have the capacity to consent, then their LAR will consent on their behalf.
 - The caregiver will also be asked to consent to a HIPAA authorization form as some of the assessments address their own personal health. In addition they will agree that data collected by the research team can be used for the purposes of research.
- If consent by LAR is necessary, the study team will also seek a separate assent to participate from the individual with aMCI or AD. If an assent isn't obtained, an audible dissent will be honored.
- The patient with aMCI or AD will not receive any assessment or participate in interviews as their participation in the study is passive. Once enrollment of the patient with aMCI or AD is complete, they have completed their portion of the study. All other activities will involve the caregiver or the caregiver monitoring the patient with aMCI or AD.

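### The one block size the protocol discloses (4) could make about a third of arm assignments predictable to recruiting staff, exposing the between-arm comparisons

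*Combined protocol and SAP*

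**What the plan says.** Section 6.4 (Randomization Scheme) allocates dyads "using a randomization list that contains group assignment in blocks". The block size appears once, as an input to the rule that limits the number of strata: "Using $n=154$ and $B=4". The protocol then sets 8 strata from diagnosis, gender and age. Section 5.0 fixes 1:1 allocation, 77 dyads per group, and Table 1 answers no to "Multiple Site Trial".

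On concealment, section 6.4 says: "Sealed envelopes with randomization assignments will be prepared by a research team member not involved" with enrollment, working from the biostatistician's calculations and instructions. The documents do not mention varying block sizes, keeping the size from recruiters, opaque or numbered envelopes, or central release of assignments.

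The arms are visibly different. Section 5.0 states: "The control group will not receive the BCN intervention". No masking of staff or caregivers is described. In section 7.0, study team members telephone dyads, explain the study and schedule the consent call. Team members also deliver the supply bin, which can contain a loaner phone: "If the dyad has been randomized to Group 2- The Three Assessments and Mobile Application and request to use a study mobile phone". Diagnosis and date of birth are taken from the patient's record before first contact.

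**The concern.** Blocking forces the arms back into balance at the end of every block. Anyone who knows the block size and the assignments made so far in a stratum can work out some of the next ones. Independent preparation of the envelopes protects the list itself, but not against this deduction.

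The conditions for making the deduction are present here. The size is in the protocol, one clinic supplies every dyad, and assignments become visible to the team. Section 12.4 plans about 6 enrolments a month, slow enough to count by hand. Diagnosis and age group are known before the first call, if the strata refer to the patient. Staff who foresee the next arm could bring forward or delay an approach or a consent call for a particular dyad.

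At stake is selection bias between intervention and control. It matters most where the outcome is the caregiver's own rating: response burden, the NPI-Q severity and distress thresholds that define actionable data, and the NPI-Q, PSS-14 and ZBI scores.

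**Working it through.** **Inputs.** Block size 4 and 8 strata (section 6.4); 1:1 allocation (section 5.0); 154 dyads (sections 5.0 and 12.4); 70.4% of clinic patients female (section 6.3). Two inputs are assumptions, because the documents do not give them: AD share 50–90%, and share aged 65 or over 80–95%. The recruiter is assumed to know the block size, see every earlier assignment and count each stratum separately.

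**The plan's own figure.** The strata limit is n/(B × 4) = 154/(4 × 4) = 9.6. The protocol states fewer than 9 and uses 8. So 4 is the size the plan calculates with. The documents give no predictability figure.

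**Certain assignments, complete blocks.** A 2+2 block has six orders. An assignment is certain once one arm has used both its places.
- AABB and BBAA: 2 certain positions each.
- ABAB, ABBA, BAAB and BABA: 1 each.
- Share: (2 × 2 + 4 × 1)/(6 × 4) = 8/24 = 33.3%, and 154/3 = 51 dyads.

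**Certain assignments, with unfilled last blocks.** A stratum with 4q + r dyads has an expected 4q/3 certain assignments, plus 1/3 if r = 3. Averaging over simulated splits of 154 dyads into 8 strata gives 31.2% to 31.5% across the assumed shares, about 48 dyads.

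**Best guess.** Always guess the arm that is behind. The chance of being right at positions 1 to 4 is 1/2, 2/3, 2/3 and 1. The sum is 17/6, so the rate is 17/24 = 70.8%, against 50% by chance.

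**Varied sizes.** Take sizes drawn with equal probability, with the recruiter knowing the set but not the order. For a block of 2m, the expected number of correct guesses is m + ½(4^m / C(2m,m) − 1): 1.5 for size 2, 2.83 for size 4 and 4.1 for size 6. Long-run rates are:
- {2,4}: (1.5 + 2.83)/6 = 72.2%
- {4,6}: (2.83 + 4.1)/10 = 69.3%
- {2,4,6}: (1.5 + 2.83 + 4.1)/12 = 70.3%

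For {2,4}, an imbalance of 2 proves the block is a 4, and the next two assignments are then certain. This happens in one third of 4-blocks, so the certain share is (2 × 1/3)/6 = 11.1%. The other certain shares come from a simulation that updates the recruiter's knowledge after each assignment, run for a stratum of 20 and for one list of 154.

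| Sizes | Certain | Best guess |
|---|---|---|
| 4, fixed | 33% | 71% |
| {2,4} | 10–11% | 72% |
| {4,6} | 5–6% | 69% |
| {2,4,6} | about 4% | 70% |

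**The case against.** The strongest reply is that the protocol never says the list uses fixed blocks of 4. The number appears only in the strata calculation, and the envelopes follow the biostatistician's instructions, which are not in the documents. This stands as a limit on certainty: fixed blocks are an inference. But 4 is the only size given, and nothing points to variation.

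A second reply is that prediction takes effort and steering is constrained. The recruiter would need eight running counts. Section 7.0 also puts several steps between identification and enrolment: a generated list, provider notice with a week to respond, a call, mailed forms and a scheduled consent call. This makes steering harder but does not exclude it, because staff still choose when to call and when to schedule consent.

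A third reply is that much of the trial is untouched, and this stands. App completion, the usability scale and the post-intervention survey belong to the intervention arm only. The weekly-versus-monthly contrast is within dyads. Completion rates are task counts, not caregiver ratings. The Aim 3 symptom comparison is exploratory and adjusted for baseline score and covariates (section 12.3), although adjustment removes only the selection that those covariates capture.

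A reader might infer that recruiters do know a third of assignments, or that concealment has failed. The documents do not support that: they contain no evidence of counting or steering, and they do not say how many people recruit. A reader might also infer that every outcome is at risk. The limits just listed rule that out.

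**Conclusion.** The point holds as an inexpensive improvement to the design. If blocks are fixed at 4 and a recruiter knows this, sees earlier assignments and counts by stratum, 31–33% of assignments (about 48–51 of 154) are knowable beforehand and about 71% can be guessed. Those conditions, and the absence of masking, are read from the design and from what the documents leave unsaid.

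The exposed analyses are the Aim 1 response-burden comparison, the Aim 2 intervention-versus-control test, and the exploratory Aim 3 tests of NPI-Q total, NPI-Q distress, PSS-14 and ZBI.

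It is tempting to think that any random mix of sizes removes the problem. It does not. Sizes {2,4} would leave about 11% certain and raise best-guess accuracy to about 72%. Even the better mixes lower best-guess accuracy only slightly, so keeping the sizes from recruiters is an essential part of the remedy.

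**What to change.** For dyads still to be randomised, generate a new list with randomly ordered block sizes that include one above 4, such as {4,6} or {2,4,6}. Remove the block size from section 6.4. Hold the sizes in a document restricted to the biostatistician and the person who prepares the envelopes, and say in the protocol only that sizes vary and are withheld from recruiting staff. Do not use {2,4}.

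The cost is a new list, a short edit to section 6.4, and slightly more possible imbalance. The largest within-stratum difference rises from 2 dyads to 3. The protocol's own strata rule shows the trade-off. With n = 154 as the protocol uses it, the limit is 154/(4 × 4) = 9.6 at the average size of {2,4,6}, 154/(5 × 4) = 7.7 at the average size of {4,6}, and 154/(6 × 4) = 6.4 if the largest size is used. With 8 strata kept, {2,4,6} therefore sits closer to the rule.

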7.0 Study Procedures

- Subjects will be identified from a list generated with patients who receive care at the Eskenazi Health, Sandra Eskenazi Center for Brain Care Innovation (SECBCI) and have a diagnosis of either Amnestic Mild Cognitive Impairment (aMCI) or possible or probable Alzheimer's disease (AD). Patients will also be referred by SECBCI providers. The screening portion of enrollment will be done either face-to-face in the SECBCI clinic or over the phone prior to the patient's SECBCI appointment.
- This study is seeking to recruit 154 patient-caregiver dyads (n=308 human subjects).

Inclusion Criteria:

- 1) The patient has received a diagnosis of Amnestic Mild Cognitive Impairment (aMCI) or probable or possible Alzheimer's disease (AD) and receives his or her care at the Eskenazi Health, Sandra Eskenazi Center for Brain Care Innovation.
- 2) The patient has a caregiver who is willing to participate in the study.
- 3) The caregiver is at least 18 years of age and does not have visual impairment significant enough to interfere with the use of a smartphone.
- 4) Both the patient and caregiver live in the community setting in Indiana.
- 5) In cases where the patient with AD lacks capacity to consent to research, he or she must have a legally authorized representative (LAR) to consent on his or her behalf.

- 6) In cases where the patient lacks capacity to consent to research, he or she will be given an opportunity to provide assent. If the patient is unable to provide assent, an observable dissent will be honored.
- 7) The caregiver reports having contact, in person, over the telephone or via video call with the patient with aMCI or AD at least weekly on average.

Exclusion Criteria:

- 1) History of serious mental illness (schizoaffective disorder, schizophrenia, bipolar disorder)
- 2) The participant is participating in another caregiver intervention research study
- 3) The participant lacks both the capacity to consent and a legally authorized representative (LAR)
- 4)
- 4.) The potential participant with a diagnosis of either aMCI or AD communicates observable dissent.
- 5) 5.) The patient lives in a long-term care facility.

- Using this research subject list the research team will access the patient electronic medical record to obtain contact information and other necessary screening data elements. This will be recorded on paper and destroyed as soon as the dyad declines interest in the study. If the subjects are enrolled in the study then this data will be inputted into a REDCap database.
- Data Elements to be pulled from patient's record prior to screening
 - 1) Patient name, DOB, MRN and contact information
 - 2) Primary caregiver name and contact information
 - 3) Diagnosis of either aMCI or possible or probable AD.
 - 4) Associated SECBCI physician name
 - 5) Most recent SECBCI visit date
 - 6) Next scheduled SECBCI visit date
 - 7) Most recent MMSE score and date
- Once an eligible patient has been identified the study team member will notify the respective SECBCI provider, that their patient will be approached for recruitment and request their' opinion of the patient's capacity to consent to research. The study team member will allow a week for the provider to respond before moving forward with contacting the patient-caregiver dyad. Only study team members will have access to the patient list. All study team members have completed CITI training.
- The study team member will attempt to contact the patient-caregiver dyad by phone to see whether they would be interested in learning more about and possibly participating in the research study. A verbal recruitment screener will be used.
- The study team member will explain the study and review the informed consent process. If both the patient and caregiver are interested they will proceed with scheduling a time for the patient-caregiver dyad to talk over the phone to conduct the informed consent review. At that time the research team member will mail out copies

of the informed consent and assent, the HIPAA authorization form, and the COVID-19 risk handout. This handout will inform the patient and caregiver of the risks related to COVID-19 which should help them when making the decision to meet in person or complete the assessments over the phone.

- The informed consent document and HIPAA authorization form will be reviewed over the telephone, rather than in-person, to minimize COVID-19 exposure. Once the participants have had time to ask questions and their understanding of the study is assessed, verbal consent will be attained. At this point in time, the study team member will ask the caregiver their appointment type preference, whether they want to meet in person the Eskenazi Health, Fifth Third Building or complete the assessments over the phone.
- Before verbal consent is obtained, the patient will be assessed to determine their capacity to consent to research.
 - The provider reports the patient lacks the capacity to consent.
 - The MMSE score is ≤ 17
 - If neither of the aforementioned measures have been met, the study team will ask the patient the following 4 questions:
 - What do you understand is wrong with your brain health right now?
 - Can you please explain in your own words the choices I have presented to you (choice to consent)?
 - If you decide to participate in this study, what good things might happen and what harm might occur?
 - Can you please explain how you decided to participate (or not participate) in this study?
 - The determination to have the capacity to consent to research the patient must answer these 4 questions correctly.
 - The patient's Legal Authorized Representative (LAR) will consent on the patient's behalf if any of the following conditions are met:
 - The patient lacks the capacity to consent to research.
 - The patient is unable to communicate verbally or through another method due to the progression of their disease.
 - The patient has a court appointed guardian.

As a part of the informed consent process, once capacity to consent has been established, the study team member will ask four teach back questions related to the study to both the caregiver and the patient. These questions are asked to ensure the caregiver and patient understand what they are consenting to, as well as making them aware that we have safety procedures in place to minimize their exposure to COVID-19.

 - If the caregiver chooses to complete the assessments remotely, the study team member will schedule a time to deliver study supplies. Regardless of what

randomization group they are in, the study team member will deliver a plastic bin which contains a binder with paper copies of the assessments and other study related materials. It will be delivered to the patient and caregiver's respective homes without direct contact from team members (left outside home). If the dyad has been randomized to Group 2- The Three Assessments and Mobile Application and request to use a study mobile phone, this will be included in the plastic bin. The purpose of the study binder is to ensure the dyad is able to follow along during the assessment. The study team members will have a mirror binder where they will indicate the caregiver's responses to the assessment questions.

- The study team member will then arrange a time for the caregiver to complete the baseline study visit. The baseline study visit will be completed over the telephone or if the caregiver prefers in-person at the Eskenazi Health, Fifth Third Building located on the Eskenazi Health Hospital Campus (the in-person visit is entirely optional).
- The patient will not be present or participate in the baseline, 3-month or Final / 6-month research visit.
 - During the informed consent visit, patients who have the capacity to consent will consent to the HIPAA authorization form, which grants the study team permission to access their Eskenazi Health medical record and to communicate with their SECBCI clinical team. If they do not have the capacity to consent, then their LAR will consent on their behalf.
 - The caregiver will also be asked to consent to a HIPAA authorization form as some of the assessments address their own personal health. In addition they will agree that data collected by the research team can be used for the purposes of research.
- If consent by LAR is necessary, the study team will also seek a separate assent to participate from the individual with aMCI or AD. If an assent isn't obtained, an audible dissent will be honored.
- The patient with aMCI or AD will not receive any assessment or participate in interviews as their participation in the study is passive. Once enrollment of the patient with aMCI or AD is complete, they have completed their portion of the study. All other activities will involve the caregiver or the caregiver monitoring the patient with aMCI or AD.
- Once enrollment is complete the study team member will schedule and conduct the baseline research visit with the caregiver and provide education to the caregiver about Behavioral and Psychological Symptoms of Dementia (BPSD).
- If the participants choose to complete their assessment in person, then the study team member will call 24-48 hours before the baseline visit to make sure that in the past 2 weeks the patient and caregiver have not been in contact with anyone diagnosed with COVID-19, and have not developed any symptoms to suggest that

they currently have COVID-19. If they choose to complete their assessment over the telephone, then the study team will not make this call.

- If either the patient or caregiver have had a recent COVID-19 exposure or symptoms of COVID-19 then the research visit will be rescheduled and the patient and/or caregiver will be referred to resources to help address the patient's or caregiver's COVID-19 exposure and/or symptoms.
- The study team will follow Eskenazi Health policy by wearing a mask and gloves during any in-person research visit.
- The study team will sanitize all research supplies and research visit space before and after every research visit.
- **The baseline visit includes completion of the following (+/- 14 days from enrollment) and will be conducted over the phone or in-person at the Eskenazi Health, Fifth Third Building on the Eskenazi Health Hospital Campus. The in-person visit option is entirely optional and is based on the caregiver's expressed preference. COVID-19 safety and cleaning procedures are listed on page 22 of this protocol. Explanations that older adults and individuals with underlying health conditions are at greater risk for contracting COVID-19 and for having more severe health problems from COVID-19 if they contract the illness, including death, are outlined in the consent/assent:**
 - 1) Single Item Literacy Screener (SILS)
 - 2) Motivations and Barriers Survey
 - 3) Dyad Demographics
 - 4) Neuropsychiatric Inventory Questionnaire (NPI-Q)
 - 5) Perceived Stress Scale 14 (PSS-14)
 - 6) Zarit Burden Interview (ZBI)
 - 7) COVID-19 Physical & Mental Health Questionnaire
 - 8) Senior Technology Acceptance Form
 - 9) Caregiver & Environment Assessment of Neuropsychiatric Symptoms (CEAN)
 - 10) Caregiver Pre-Intervention Semi-Structured Interview
 - 11) Provision of education on BPSD
 - 12) Provision of a \$10 Kroger gift card to both the patient and caregiver following completion of the baseline visit activities.
 - 13) Provision of an Eskenazi Health parking voucher (only if the visit takes place in-person).
- The caregiver in the intervention group will be asked to complete a survey on Behavioral and Psychological Symptoms of Dementia (BPSD) for the person with aMCI or AD for 6 months through either the caregiver's smartphone or a loaner smartphone from the study. The survey is a mobile health version of the

Neuropsychiatric Inventory – Questionnaire (NPI-Q) delivered by the Brain CareNotes (BCN) app. The following additional survey question will be asked following delivery of the NPI-Q, *“How burdensome was completion of the prior scale? (Answer options: not at all burdensome, mildly burdensome, moderately burdensome, or extremely burdensome)”*

- Clinically Significant BPSD will be defined as when any NPI-Q severity domain = 3 regardless of caregiver distress, or whenever NPI-Q caregiver distress is marked as “moderate” “severe” or “very severe”.
-
- When Clinically significant BPSD is present at either the baseline visit, 3-month visit, final (6-month) visit or through completion of a BCN app record then the following actions will be triggered:
 - 1) Automatic free response follow-up questions (via BCN).
 - 2) Automatic notification of study team.
 - 3) Automatic notification of SECBCI clinical team.
 - 4) The research team to contact the caregiver and complete a semi-structured interview and the Caregiver & Environment Assessment for Neuropsychiatric Symptoms.
 - 5) The study team member documents findings and notifies PI and SECBCI clinical team.
- If the participants choose to complete their assessment in person then the study team will call 24-48 hours before the 3-month visit to make sure that in the past 2 weeks the patient and caregiver have not been in contact with anyone diagnosed with COVID-19, and have not developed any symptoms to suggest that they currently have COVID-19. If they choose to complete their assessment over the telephone, then the study team will not make this call.
- **The 3-month assessment visit occurs 3 months from their baseline completion (+/- 14 days) includes completion of the following, and will be conducted over the phone or in-person at the Eskenazi Health, Fifth Third Building on the Eskenazi Health Hospital Campus. The in-person visit option is entirely optional and is based on the caregiver’s expressed preference. COVID-19 safety and cleaning procedures are listed on page 22 of this protocol. Explanations that older adults and individuals with underlying health conditions are at greater risk for contracting COVID-19 and for having more severe health problems from COVID-19 if they contract the illness, including death, are outlined in the consent/assent:**
 - 1
 - 2)
 - 3)
 - 4) Neuropsychiatric Inventory Questionnaire (NPI-Q)

- 5) Perceived Stress Scale 14 (PSS-14)
- 6) Zarit Burden Interview (ZBI)
- 7) COVID-19 Physical & Mental Health Questionnaire
- 8) Senior Technology Acceptance Form
- 9) Caregiver & Environment Assessment of Neuropsychiatric Symptoms (CEAN)
- 10) System Usability Scale (SUS) – only administered to the intervention group
- 11) Caregiver Post-Intervention Survey – only administered to the intervention group
- 12) Caregiver Pre-Intervention Semi-Structured Interview
- 13) Provision of an Eskenazi Health parking voucher (only if the visit takes place in-person).

- Clinically Significant BPSD will be defined as when any NPI-Q severity domain = 3 regardless of caregiver distress, or whenever NPI-Q caregiver distress is marked as “moderate” “severe” or “very severe”.
- When Clinically significant BPSD is present at either the baseline visit, 3-month visit, final (6-month) visit or through completion of a BCN app record then the following actions will be triggered:
 - 1) Automatic free response follow-up questions (via BCN).
 - 2) Automatic notification of study team.
 - 3) Automatic notification of SECBCI clinical team.
 - 4) The research team to contact the caregiver and complete a semi-structured interview and the Caregiver & Environment Assessment for Neuropsychiatric Symptoms.
 - 5) The study team member documents findings and notifies PI and SECBCI clinical team.
- The study team will call 24-48 hours before the final / 6-month visit to make sure that in the past 2 weeks the patient and caregiver have not been in contact with anyone diagnosed with COVID-19, and have not developed any symptoms to suggest that they currently have COVID-19.
- **Final / 6-month visit occurs from the completion of their 6 month participation (+/- 14 days) includes completion of the following, and will be conducted over the phone or in-person at the Eskenazi Health, Fifth Third Building on the Eskenazi Health Hospital Campus. The in-person visit option is entirely optional and is based on the caregiver’s expressed preference. COVID-19 safety and cleaning procedures are listed on page 22 of this protocol. Explanations that older adults and individuals with underlying health conditions are at greater risk for contracting COVID-19 and for having more severe health problems from COVID-19 if they contract the illness, including death, are outlined in the consent/assent:**
 - 1) Caregiver is asked to return the loaner phone or where personal phone is used the Brain CareNotes app will be uninstalled.

- 2) Neuropsychiatric Inventory Questionnaire (NPI-Q)
- 3) Perceived Stress Scale 14 (PSS-14)
- 4) Zarit Burden Interview (ZBI)
- 5) Caregiver & Environment Assessment of Neuropsychiatric Symptoms (CEAN)
- 6) COVID-19 Physical & Mental Health Questionnaire
- 7) Senior Technology Acceptance Form
- 8) System Usability Scale (SUS) – only administered to the intervention group
- 9) Caregiver Post-Intervention Survey – only administered to the intervention group
- 10) Caregiver Post-Intervention Semi-Structured Interview
- 11) Provision of a \$10 Kroeger gift card to the caregiver after completion of final visit activities.
- 12) Provision of an Eskenazi Health parking voucher (only if the visit takes place in-person).

- Once the final visit has been completed and the caregiver has received the \$10-dollar Kroger gift card for their time, participation in the study will be complete.
- All semi-structured interviews will be audio recorded, stored securely, and transcribed. Once transcribed audio recordings will be destroyed.
- For every remote assessment, baseline/ 3-month/ 6-month, the research team will follow the COVID-19 safety precautions, which includes donning proper PPE and cleaning procedures.
 - If the subject requests a remote assessment, the research team member delivers and retrieves the supply box; the team member will don gloves and a mask during the respective transaction.
 - If the team member has retrieved the supply box they will put the supply box into another plastic bin, and load it into the trunk of their car. It will remain there until they have the opportunity to sanitize the plastic supply box and supplies.
 - The research team members will wear gloves and use sanitizing wipes and/or a prepared bleach solution with paper towels.
 - They will dispose of contaminated materials into a plastic bag and throw it away.
 - Once all of the supplies have been sanitized, the research team member will wash their hands thoroughly for a minimum of 20 seconds.
- For every in-person assessment, baseline/ 3-month/ 6-month, the research team will follow the COVID-19 safety precautions, which includes donning proper PPE and cleaning procedures. The research visits as well as the safety procedures have been reviewed and approved by Eskenazi Health.
 - If the subject is comfortable with being seen in person at the Fifth Third Building, the research team member will call the day before and the day of to screen the subject for any COVID-19 related symptoms.
 - If the subject responds “YES” then the assessment will be rescheduled. If the subject responds “NO” then they can proceed with the appointment.

- On the day of the appointment, the research team member will don a mask and wear gloves throughout the assessment. They will also request the subject wear a mask. If the patient/caregiver dyad doesn't bring one with them or isn't provided one upon arrival to Eskenazi Health, the study team will provide the mask for them. The dyad will also receive a parking voucher for their time spent with the research team member.
- If the subject has a cough, that is not COVID-19 related, the research team member will be required to wear a gown and face shield.
- All cleaning procedures remain the same.

